4.2 Def 4.3 Stu 4.4 Ana 4.5 Mis	a Sources inition of Baseline and Change from Baseline dy Day lysis Visit Window sing Data and Partial Dates tiple Study Centers	11 11 11
5.Statistical A	nalysis	12
5.2 Ana 5.2.1	othesis testing alysis Populations Screened Analysis Set Full Analysis Set (FAS) Safety Analysis Set Per Protocol (PP) Analysis Set	12 13 13 13
6.Data Displa	y Characteristics	14
	oject Accountability Disposition Subject Characteristics Protocol Deviations and Population Inclusions	14 15
7.Efficacy Ana	alyses	16
7.1.1 7.1.2 7.1.3 7.1.4 7.1.5	tistical Models MMRM analysis GEE model Logistic regression model ANCOVA model Bayesian analysis cacy endpoints Vineland Adaptive Behavior Scales, 3rd Edition (VABS-3) Aberrant Behavior Checklist (ABC)	16 17 18 18 18

7.2.3 Clinical Global II	mpression – Severity and Improvement (CGI-	-S and CGI
I) 19		
7.3 Exploratory Analyses	s	20
7.3.1		20
7.3.2		20
7.3.3		 21
7.3.4		22
7.3.5		22
7.3.6		23
8.Safety Analyses		23
8.1 Exposure and treatm	nent compliance	23
8.2 Adverse Events		24
8.2.1 Adverse Events	of Special Interest	26
8.3 Clinical Laboratory F	Results	26
8.4 Vital Signs		27
8.5 Physical Examinatio	n	28
8.612-lead ECG		28
8.7 C-SSRS		28
8.8 Concomitant Medica	tions and Concomitant Therapy	28
8.9 Pregnancy monitoring	ng	29
Changes from the Protocol Pla	nned Analysis	30
References		31

1. Introduction

[figure not shown]
The protocol for study GWND19189 describes the general approach to analysis of data from the study. This analysis plan describes in detail the statistical methodology and planned analyses to be conducted for Protocol GWND19189 for inclusion in the CSR. Specifications for tables, figures, and listings are in a separate document.

2. Protocol Objectives and Endpoints

The objectives and endpoints for the study are outlined in Table 1.

Table 1 Protocol Objectives and Endpoints

Objectives	Endpoints
Efficacy	
To evaluate the efficacy of GWP42003-P, compared with placebo, in reducing symptom severity in children and adolescents.with ASD	Change from baseline to week 12 of the VABS-3 social and communication composite (arithmetic mean of the social and communication domain scores), the adaptive behavior composite, and individual domain scores.
	Change from baseline to week 12 of the Aberrant Behavior Checklist Subscales.
	Overall condition
	 Proportion of patients with a score of "very much improved" or "much improved" on CGI-I at week 12. Proportion of patients with a score of "very much improved", "much improved" or "minimally improved" on CGI-I at week 12. Change from baseline to week 12 of the CGI-S score.
Safety	
To evaluate the safety of GWP42003-P compared with placebo in children with ASD	Adverse events Clinical laboratory parameters Vital signs Physical examination procedures 12-lead ECG C-SSRS

3. Study Design

3.1 Design Overview

This is an exploratory, Phase 2, double-blind, randomized, placebo-controlled, multisite trial, which will compare the safety and efficacy of a 10 mg/kg/day dose of GWP42003-P versus placebo in children and adolescents with ASD.

Approximately 160 subjects who meet eligibility criteria and consent to participate in the study are randomly assigned in a 1:1 ratio to one of the following treatment groups:

- GWP42003-P
- Placebo

Patients will be stratified based on their age (6 to 11, 12 to 17), use of antipsychotics (on versus off), and region (North America versus Rest of the World). Patients will be administered 5 mg/kg/day GWP42003-P or matching volumes of placebo for 1 week and then 10 mg/kg/day GWP42003-P or matching volumes of placebo for 11 weeks. At the end of treatment, patients will taper the medication over 1 week.

Overall trial design is outlined in Figure 1.

[figure not shown]

[figure not shown]
Figure 1 Trial Design and Treatment Schematic

Eligible patients may be randomized 7 to 14 days after the screening visit (Visit 1), once all required assessments have been completed and laboratory results have been reviewed; if required, screening assessments may be split over 2 visits; however, both visits must fall into the 7 to 14 day window prior to randomization (Visit 2). One week and 2 weeks following randomization, there will be 2 safety telephone visits (Visit 3 and 4). The patient will return to the clinic or video call and home nurse visit, 4 weeks after randomization (Visit 5). Six weeks after randomization, there will be another safety call (Visit 6), and then the patient will return for a clinic visit or video call visit (Visit 7) 8 weeks after randomization. The end of treatment visit will take place 12 weeks after randomization (Visit 8). If at any point it is decided to withdraw a patient from the trial, the patient should return to the clinic as soon as possible and complete Visit 8 procedures. At Visit 8, patients will commence to taper the medication (unless in case of withdrawal the medication was already discontinued or continued dosing is inadvisable, e.g., due to an AE). At the end of taper, the patient will return to the clinic or video call and home nurse visit (Visit 9). All patients will have a follow-up safety telephone visit, 14 days after Visit 9 or Visit 8 (in case the patient did not taper the medication).

Visit windows are allowed as defined in the schedule of assessment. Visit 3, 4, 5, 6, 7, and 8 days and windows are counted from the day of randomization (Visit 2). Visit 9 day and window is counted from the day of Visit 8. Visit 10 day and window is counted from the day of Visit 9, or the day of Visit 8 (if the patient did not enter the taper period).

3.2 Sample Size

3.3 Treatment Randomization

A permuted block randomization scheme was created to assign subjects in a 1:1 ratio to either of the two treatment groups. The scheme was stratified by age (6 to 11 years; 12 to 17 years), use of anti-psychotics (on; off), and region (North America; Other). At visit 2, randomization will be performed for each consenting eligible subject using

3.4 Assessment Schedule

The assessments and procedures that will be conducted during this study are presented in the Schedule of Assessments (SoA) in Appendix 1 of the study protocol.

3.5 Interventions

GWP42003-P or placebo will be administered orally b.i.d. (morning and evening) using the syringe(s) provided, preferentially with food i.e., within 30 minutes after the end of a meal/snack. The first dose of GWP42003-P or placebo is taken at home in the evening. The time of IMP administration in relation to food should be kept consistent throughout the trial.

Patients will be administered 5 mg/kg/day GWP42003-P or matching volumes of placebo for 1 week and then 10 mg/kg/day GWP42003-P or matching volumes of placebo for 11 weeks. At the end of treatment, patients will taper the medication in steps of -2.5 mg/kg/day every 2 days over 1 week.

4. General Study Level Considerations

4.1 Data Sources

Data are recorded on electronic case report forms (eCRFs). Central laboratory data and will be provided via electronic data transfers. Electronic devices are used to capture dosing diary, medications, and questionnaire data.

Section 16.3 of the protocol provides additional details describing data collection.

4.2 Definition of Baseline and Change from Baseline

Baseline for analysis purposes is defined as the last available observation prior to the first administration of the study drug at home in the evening of Visit 2.

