4 EXPERIMENTAL PLAN

4.1 Trial Design

This is an exploratory, Phase 2, double-blind, randomized, placebo-controlled, multisite trial, which will compare the safety and efficacy of a 10/mg/kg/day dose of GWP42003-P versus placebo in children and adolescents with ASD.

Patients will be screened and if they meet eligibility criteria will be randomized to receive GWP42003-P or matching placebo in a 1:1 ratio. Patients will be stratified based on their age (6 to 11, 12 to 17), use of antipsychotics (on versus off), and region (North America versus Rest of the World). Patients will be administered 5 mg/kg/day GWP42003-P or matching volumes of placebo for 1 week and then 10 mg/kg/day GWP42003-P or matching volumes of placebo for 1 weeks. At the end of treatment, patients will taper the medication over 1 week.

A schematic (Figure 1-1), presented at the end of Section 1, depicts the overall trial design. More detailed information on treatment and trial procedures is provided in Section 8 and Section 9, respectively.

Eligible patients may be randomized 7 to 14 days after the screening visit (Visit 1), once all required assessments have been completed and laboratory results have been reviewed; if required, screening assessment may be spilt over 2 visits; however both visits must fall into the 7 to 14 day window prior to randomization (Visit 2). One week and 2 weeks following randomization, there will be 2 safety telephone visits (Visit 3 and 4). The patient will return to the clinic or video call and home nurse visit, 4 weeks after randomization (Visit 5). Six weeks after randomization, there will be another safety call (Visit 6), and then the patient will return for a clinic visit or video call visit (Visit 7) 8 weeks after randomization. The end of treatment visit will take place 12 weeks after randomization (Visit 8). If at any point it is decided to withdraw a patient from the trial, the patient should return to the clinic as soon as possible and complete Visit 8 procedures. At Visit 8, patients will commence to taper the medication (unless in case of withdrawal the medication was already discontinued or continued dosing is inadvisable, e.g., due to an AE). At the end of taper, the patient will return to the clinic or video call and home nurse visit (Visit 9). All patients will have a follow-up safety telephone visit, 14 days after Visit 9 or Visit 8 (in case the patient did not taper the medication).

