- 6.2.18 Patient has received an IMP within the 12 weeks prior to the screening visit.
- 6.2.19 Patient had brain surgery or traumatic brain injury within 1 year of screening.
- 6.2.20 Patient has any other significant disease or disorder which, in the opinion of the investigator, may either put the patient, other participants, or site staff at risk because of participation in the trial, may influence the result of the trial, or may affect the patient's ability to take part in the trial.

- 6.2.21 Any abnormalities identified following a physical examination of the patient that, in the opinion of the investigator, would jeopardize the safety of the patient if they took part in the trial.
- 6.2.22 Any history of suicidal behavior (lifelong) or any suicidal ideation of type 4 or 5 on the C-SSRS in the last 4 weeks or at screening or randomization.
- 6.2.23 Patient has donated blood during the past 12 weeks and is unwilling to abstain from donation of blood during the trial.
- 6.2.24 Patient has any known or suspected history of alcohol or substance abuse or positive drugs of abuse test at screening (not justified by a known concurrent medication).
- 6.2.25 Patient has previously been randomized into this trial.
- 6.2.26 Patient has plans to travel outside their country of residence during the trial, unless the patient has confirmation that the IMP is permitted in the destination country/state.

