4.4 Analysis Visit Window

No analysis visit windowing will be performed for this study.

For by-visit summaries, data recorded at the nominal visit will be presented. Subjects who withdraw early will be mapped to the nearest scheduled visit considering missed previous visits (if previous visit is not missing, then consider the next visit). Unscheduled measurements will not be included in by-visit summaries but will contribute to the baseline timepoint (if baseline is missing) and/or worst-case value where required (e.g. shift tables or summaries involving worst-case values at any time post-Baseline).

Listings will include scheduled, unscheduled, retest and early discontinuation data.

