8.7 C-SSRS

The C-SSRS is a suicide risk assessment performed by the investigator at Visit 1 (Screening), Visit 2, Visit 5, Visit 7, Visit 8 EoT/WD, and Visit 9.

The number and percent of subjects with suicidal ideation by category, suicidal behavior by category and/or self-injurious behavior without suicidal intent will be tabulated. Percentages will be based on the number of subjects with at least one post-baseline C-SSRS assessment.

Shift from baseline showing any change in suicidal ideation and suicidal behavior will be provided. Subjects will be summarized under the worst of the following three categories: 1) No suicidal ideation of behavior; 2) suicidal ideation only; 3) suicidal ideation and behavior.

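### The C-SSRS shift table uses one pre-dose assessment, normally Visit 2, as baseline, so lower-type ideation recorded at Visit 1 can be tabulated as newly emergent if it is absent at Visit 2 and recurs after dosing

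*SAP*

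**What the plan says.** SAP 4.2 gives a single general baseline: "Baseline for analysis purposes is defined as the last available observation prior to the first administration of the study drug". The first dose is taken at home on the evening of Visit 2.

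SAP 8.7 schedules the C-SSRS "at Visit 1 (Screening), Visit 2, Visit 5, Visit 7, Visit 8 EoT/WD, and Visit 9", and the protocol's Appendix 1 shows the same visits. Two assessments therefore precede dosing, and four scheduled ones follow it.

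SAP 8.7 plans this display: "Shift from baseline showing any change in suicidal ideation and suicidal behavior will be provided". It adds: "Subjects will be summarized under the worst of the following three categories". The categories are no ideation or behavior, ideation only, and ideation with behavior. The section defines no baseline specific to the C-SSRS. It does not itself say that the worst category is taken across visits. That comes from SAP 4.4, under which unscheduled measurements contribute to the "worst-case value where required (e.g. shift tables or summaries involving worst-case values at any time post-Baseline". Before dosing, an unscheduled measurement counts only if baseline is missing.

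Protocol criterion 6.2.22 excludes any lifelong suicidal behavior and "any suicidal ideation of type 4 or 5 on the C-SSRS in the last 4 weeks or at screening or randomization". Ideation of types 1 to 3 does not exclude. Protocol 4.1 places Visit 2 at 7 to 14 days after Visit 1.

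**The concern.** Ideation can come and go. A last-observation baseline suits a measure that is present at every visit. It suits less well an intermittent event that is then set against the worst of several later looks. Here one pre-dose look is compared with up to four scheduled post-dose looks or more, and a second pre-dose look that has already been collected is left out. A patient whose ideation was on record before dosing can then sit in the same cell as one whose ideation first appeared on treatment.

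Protocol 3.3.2 lists suicidal behavior and ideation among the warnings established for this drug, and the C-SSRS is a named safety endpoint. The shift table is the only C-SSRS display in SAP 8.7 that relates post-dose findings to the pre-dose state, so it is where a reader will look for emergence.

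**Working it through.** The documents state no figure on this point, so there is none to reproduce. The check has two parts.

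**What the rules do together**

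- Pre-dose assessments collected: 2 (Visits 1 and 2). Used as baseline: 1, normally Visit 2. Visit 1 serves only if Visit 2 is missing, which is unlikely because eligibility refers to the C-SSRS at randomization.
- Scheduled post-dose assessments feeding the worst category: 4 (Visits 5, 7, 8 and 9), or 3 for a patient who does not taper and so skips Visit 9. Unscheduled assessments add to this.
- Take a child with type 2 ideation at Visit 1, none at Visit 2 and type 2 at Visit 7. The child is eligible under 6.2.22. The baseline category is none and the worst post-dose category is ideation only, so the table shows a shift from none to ideation.

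**How large this could be**

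Assume no true change over time, so that every apparent shift is background. Let p be a patient's chance of reporting ideation at any one visit. Apparent new cases need none at baseline and at least one positive among four later visits:

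- Visit 2 baseline: E[(1−p)] − E[(1−p)^5]
- Worst of Visits 1 and 2 as baseline: E[(1−p)^2] − E[(1−p)^6]

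The difference between the two is the probability of ideation at Visit 1, none at Visit 2 and recurrence. For within-patient correlation ρ, let p follow a beta distribution with mean m, a = m(1/ρ − 1) and b = (1 − m)(1/ρ − 1). Then E[(1−p)^k] is the product of (b + j)/(a + b + j) for j = 0 to k − 1. Both m and ρ are assumptions. The only document input is the scale, 72 evaluable patients per arm (Protocol 13.1).

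Worked case, m = 0.05 and ρ = 0.5, so a = 0.05 and b = 0.95:

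- E[(1−p)^k] for k = 1, 2, 4, 5, 6 is 0.9500, 0.9263, 0.8994, 0.8904, 0.8830.
- Visit 2 baseline: 0.9500 − 0.8904 = 0.0596, or 4.29 per 72.
- Worst of Visits 1 and 2: 0.9263 − 0.8830 = 0.0432 (from unrounded values), or 3.11 per 72.
- Share of apparent new cases with ideation at Visit 1: (0.0596 − 0.0432)/0.0596, about 27%.
- Apparent improvement (ideation at Visit 2, none at all four later visits): 0.8994 − 0.8904 = 0.0090. With no true change, the table shows 6.0% worsening against 0.9% improving.

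| Mean rate per visit | ρ | New per 72, Visit 2 baseline | New per 72, worst of Visits 1 and 2 | Share with ideation at Visit 1 |
|---|---|---|---|---|
| 2% | independent | 5.48 | 5.37 | 2% |
| 2% | 0.3 | 2.84 | 2.29 | 20% |
| 2% | 0.5 | 1.79 | 1.32 | 27% |
| 2% | 0.7 | 0.98 | 0.67 | 32% |
| 5% | independent | 12.69 | 12.05 | 5% |
| 5% | 0.3 | 6.73 | 5.32 | 21% |
| 5% | 0.5 | 4.29 | 3.11 | 27% |
| 5% | 0.7 | 2.36 | 1.59 | 32% |
| 10% | independent | 22.28 | 20.06 | 10% |
| 10% | 0.3 | 12.28 | 9.42 | 23% |
| 10% | 0.5 | 7.94 | 5.65 | 29% |
| 10% | 0.7 | 4.42 | 2.95 | 33% |

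At ρ = 0.5 the wider baseline removes about 0.5, 1.2 and 2.3 apparent cases per 72 at the three rates. The rest remain, because two pre-dose looks are still fewer than four post-dose looks.

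**Effect on the comparison**

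If both arms carry the same background rate c on top of emergent rates r1 and r0, the ratio becomes (r1 + c)/(r0 + c), which is nearer 1 than r1/r0. The difference stays about r1 − r0. The rule adds noise and dilutes a ratio, but does not favour either arm.

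**The case against.** The case for leaving the plan alone has weight.

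- **Three conditions must coincide.** Ideation must be present at Visit 1, absent at Visit 2 and present again after dosing. A child with ideation at both pre-dose visits is classified correctly. This stands. A reader might infer that all ideation recorded at screening is counted as new, and the documents do not support that.
- **The look-back is unknown.** Protocol 9.1.11.10 describes an interview on whether and when the patient has thought about suicide, but states no recall period for each visit. If Visit 2 looked back over four weeks, it would cover Visit 1, and the problem would largely disappear. This stands as a condition on the finding, and is itself a reason to state the period.
- **The population is selected and the table is descriptive.** Lifelong behavior, recent type 4 or 5 ideation and current major depression are excluded. No C-SSRS test is planned, both arms follow the same rule, and Visit 1 results remain in the listings. This limits the consequence but does not correct the table.
- **The present rule follows the protocol.** Protocol 13.4 uses the last pre-dose record, but allows exceptions where specified. The plan is therefore not in contradiction with itself, and an exception in the SAP needs no amendment.
- **A wider baseline can hide worsening.** A child with type 1 ideation at Visit 1, none at Visit 2 and type 5 on treatment shows as a shift today. Under a worst-pre-dose baseline the child stays within ideation only. This is a real cost. It already exists for anyone with ideation at Visit 2, and a shift by ideation type removes it.

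**Conclusion.** The point holds as a modest weakness in one descriptive safety table. Read together, SAP 4.2, 4.4 and 8.7 leave out pre-dose information that the trial collects, and can label recurrent type 1 to 3 ideation as emergent.

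The size cannot be fixed from the documents, which give no ideation rate, no within-patient correlation and no Visit 2 look-back. Under the assumed rates of 2% to 10% per visit, between 20% and 33% of apparent new cases would already have had ideation at Visit 1 for ρ of 0.3 to 0.7. If visits were independent, the share would be only 2% to 10%. A look-back at Visit 2 that reached Visit 1 would make it close to zero.

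A reader might also infer that the rule biases the comparison between arms. It does not by itself: it is applied identically to both, and its effect is to inflate each arm's count and draw a ratio toward no difference. Nor should the whole excess of apparent worsening over improvement be put down to the omitted Visit 1. Most of it comes from the larger number of post-dose looks and would remain after the change.

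**What to change.** Three additions to SAP 8.7, made before unblinding:

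1. Define the C-SSRS baseline as the worst category over all pre-dose assessments, that is, the recent period at Visit 1 together with Visit 2. Keep SAP 4.2 for every other measure.
2. State the look-back period used at Visit 2.
3. Tabulate the shift by ideation type (none, 1 to 5) as well as by the three categories, or show the version with the SAP 4.2 baseline alongside. Either keeps visible the worsening that the wider baseline would otherwise hide.

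The cost is a few sentences and a small programming change, with one more table. The data are already collected, there is no added burden on patients or sites, and no protocol amendment is needed.

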4.3 Study Day

Study day 1 is defined as the date of the first dose, and the day immediately prior to study day 1 is study day -1. For any events on or after the first administration of the study drug, study day is calculated as:

event date - date of first administration of study drug + 1.

For any events before the first administration date, study day is calculated as:

event date - date of first administration of study drug.

4.4 Analysis Visit Window

No analysis visit windowing will be performed for this study.

For by-visit summaries, data recorded at the nominal visit will be presented. Subjects who withdraw early will be mapped to the nearest scheduled visit considering missed previous visits (if previous visit is not missing, then consider the next visit). Unscheduled measurements will not be included in by-visit summaries but will contribute to the baseline timepoint (if baseline is missing) and/or worst-case value where required (e.g. shift tables or summaries involving worst-case values at any time post-Baseline).

Listings will include scheduled, unscheduled, retest and early discontinuation data.

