10 WITHDRAWAL

In accordance with the Declaration of Helsinki²⁵, the ICH Tripartite Guideline for GCP Topic $E6(R1)^{26}$, the FDA regulations relating to GCP and clinical trials^{27,28,29}, the EU Clinical Trials Directive³⁰, the EU Good Clinical Practice/GCP Directive³¹ and/or other applicable regulations, a patient has the right to withdraw from the trial at any time and for any reason, with no obligation to provide a reason, and without prejudice to his or her future medical care by the physician or at the institution.

The patient must be withdrawn from the trial if any of the following apply:

- Administrative decision by the investigator, GW, or a regulatory authority.
- Did not meet eligibility criteria.
- Pregnancy.
- Protocol deviation that is considered to compromise potentially the safety of the patient.
- Withdrawal of patient consent/assent.
- Withdrawal of parent(s)/legal representative consent.
- ALT or $AST > 3 \times ULN$ with the appearance of fatigue, nausea, vomiting, right upper quadrant pain or tenderness, fever, rash, and/or eosinophilia (> 5%).
- ALT or AST $> 8 \times ULN$.
- ALT or $AST > 5 \times ULN$ for more than 2 weeks.
- ALT or AST > $3 \times$ ULN and (TBL > $2 \times$ ULN or INR > 1.5).

Note: Prior to treatment discontinuation for the transaminase elevations noted above, the investigator may choose to confirm the transaminase elevations by repeating the following laboratory tests, tests within 24 to 48 hours: ALT, AST, TBL, INR, % eosinophils, gamma-glutamyl transferase, and alkaline phosphatase. Should the above transaminase elevation criteria be confirmed, the patient must be withdrawn from the trial. In cases where transaminase elevation withdrawal criteria are not met or confirmed, the dose of IMP or a concomitant medication with known hepatotoxicity may be reduced following discussion with the medical monitor.

• Lost to follow-up.

Patients may also be withdrawn from the trial for any of the following:

- Patient non-compliance.
- AE (including clinically significant laboratory result) which, in the opinion of the investigator, would compromise the continued safe participation of the patient in the trial.
- Patient cannot tolerate a dose level of 5 mg/kg/day.
- Any evidence of use of drugs of abuse or drug diversion.
- Suicidal ideation or behavior of type 4 or 5 during the treatment period, as evaluated with the C-SSRS.

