7.1 Statistical Models

7.1.1 MMRM analysis

The change from baseline of the VABS, ABC and RBS endpoints will be analyzed using an MMRM model. The corresponding model will include randomization stratification factors, baseline score, visit, treatment arm, visit by treatment arm interaction, visit by baseline interaction as fixed effects, and visit repeated within each patient as a repeated effect.

LS mean estimates for each treatment arm at each visit, along with the standard error and 95% CI will be presented separately. In addition, estimates of the treatment difference at each visit will be presented along with standard errors of difference and 95% CIs. The main comparison of interest is the estimate of the treatment difference at Week 12 (Visit 8).

The following provides sample code for implementing MMRM analysis using compound symetry covariance matrix:

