7.1.2 GEE model

CGI-I and the change from baseline of CGI-S endpoints will be analyzed using an GEE model. Treatment arm and stratification factors as fixed effects and baseline response as a covariate. The model will also include a repeated statement that allows to model the correlation of the dependent variable at different time points.

An ordinal multinomial distribution with cumulative logit link is assumed in the model. Parameter estimates, standard errors and 95% confidence intervals will be presented which are based on empirical standard error estimates.

The following provides sample code for implementing GEE analysis using independent covariance matrix:

```
proc genmod data=test descending;
  class subjid trt visit agegr antipmed region;
  model chg = base trt visit trt*visit base*visit randager randrgn randpsy /
  dist=multinomial
  link=clogit type3 wald;
  repeated subject=subjid / withinsubject=visit type=indep corrw covb;
```

Note: Model variables are same as in MMRM

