7.2 Efficacy endpoints

7.2.1 Vineland Adaptive Behavior Scales, 3rd Edition (VABS-3)

The Vineland-3 assesses adaptive behavior in 3 domains: Communication, Daily Living Skills, and Socialization. Each domain has 3 subdomains: receptive, expressive, written (Communication domain); personal, domestic, community (Daily Living Skills domain); interpersonal relationships, play and leisure, coping skills (Socialization domain). The assessment are done at Visit 2, Visit 5, Visit 7, and Visit 8 EoT/WD.

Subdomain and domain scores will be calculated in the Rater Station. The Chronological Age at baseline is used to derived scores for the Vineland-3 throughout the study. The social and communication composite score is a key interest and will be calculated as the arithmetic mean of the Socialization and Communication domain scores.

The adaptive behavior composite score is calculated as arithmetic mean of all 3 domain scores.

The change from baseline in subdomain, domain and composite scores will be summarized by visit. The change from baseline in social and communication composite score, adaptive behavior composite score, and individual domain scores will be analyzed using an MMRM model. Multiple analyses will carryout by including all observed data and using per protocol set. Normality assumption will be tested for Social and communication composite using Q-Q plot.

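### Does the rule that places early-withdrawal assessments at a scheduled visit leave the Week 12 comparison undefined?

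*SAP*

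**What the plan says.** SAP 4.4 (Analysis Visit Window) first rules out visit windowing. It continues: "For by-visit summaries, data recorded at the nominal visit will be presented". The sentence after that deals with early withdrawals, whose assessments are "mapped to the nearest scheduled visit considering missed previous visits (if previous visit is not missing, then consider the next visit". No maximum distance in days is given.

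These records exist because, under SAP 3.1 and Protocol 4.1, on withdrawal "the patient should return to the clinic as soon as possible and complete Visit 8 procedures". The schedule in Protocol Appendix 1 and the instrument descriptions in SAP 7.2.1 to 7.2.3 give end of treatment and withdrawal one shared label, Visit 8 EoT/WD. Visit 7 is day 57 ± 3 and Visit 8 is day 85 ± 3.

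For the MMRM, SAP 7.1.1 states: "The main comparison of interest is the estimate of the treatment difference at Week 12 (Visit 8". SAP 7.2.1 adds, for VABS-3: "Multiple analyses will carryout by including all observed data and using per protocol set". SAP 7.2.3 defines CGI-I responders by their Week 12 score. None of these sections cites 4.4.

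Two related places cannot be read here. The MMRM sample code is announced in SAP 7.1.1 but does not appear in the public text, and the GEE code refers back to it: "Note: Model variables are same as in MMRM". SAP 1 also says: "Specifications for tables, figures, and listings are in a separate document".

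**The concern.** Read alone, the mapping rule stretches the meaning of Week 12. If Visit 7 took place on day 57, an assessment on day 58 fills the Week 12 cell although it is 27 days before day 85 and one day after Week 8. The paragraph also opens with by-visit summaries, which invites the question whether the models follow the same rule.

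Three treatments of a withdrawal record can be imagined: map it under 4.4, leave it at the Visit 8 label under which it was collected, or leave it out of Week 12. If two programmers chose differently, the VABS-3 and ABC-I differences at Week 12 and the CGI-I responder counts could differ. If the drug effect builds over time, early records labelled Week 12 would also dilute the estimate.

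**Working it through.** **Inputs.** Protocol 13.1: SD 8.46, difference 4 points, 72 evaluable per arm, 160 randomized, 10% drop-out. Protocol Appendix 1: Visits 5, 7 and 8 on days 29, 57 and 85, each ± 3.

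**The plan's own figure.** Normal approximation: n = 2 × (1.960 + 0.842)² × 8.46² / 4² = 70.2, so 71 per arm. The t-based calculation gives 71.2, so 72, with power 0.804 at 72. 144 / 0.9 = 160. The plan's figures reproduce. Standard error: 8.46 × √(2/72) = 1.41.

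**Step 1: where the readings differ.** Counting only visits at which the efficacy instruments are given, and assuming earlier visits were attended:

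| Last efficacy visit attended | Mapped under 4.4 | Collected label kept |
|---|---|---|
| Visit 7 | Visit 8 | Visit 8 |
| Visit 5 | Visit 7 | Visit 8 |
| Visit 2 | Visit 5 | Visit 8 |

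The first row is the one that raises the concern, and there the two readings agree. A patient who attends Visit 7 and withdraws on day 65 with a CGI-I score of 2 is a Week 12 responder under both. Only leaving the record out would remove the score, and no section of the SAP says to do that.

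**Step 2: how many days are involved.** With Visit 7 on day 57, days 58-84 (27 days) map to Week 12. Of these, 13 (days 58-70) are nearer day 57, and 3 (days 82-84) are already inside the Visit 8 window. With Visit 7 on day 54 or day 60, the span is 30 or 24 days, with 16 or 10 nearer Week 8.

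**Step 3: how many records.** Assumptions: 16 withdrawals spread evenly over days 2-84 (83 days), 144 completers, and a share r who return. The documents do not give r. Protocol 10 lists "Lost to follow-up" among the withdrawal reasons, so r = 1 is optimistic; 0.5 to 1 is shown.

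Records mapped to Week 12: k = 16r × 27/83 = 2.60 to 5.20. From days 58-70: 16r × 13/83 = 1.25 to 2.51.

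**Step 4: effect on the VABS-3 difference**, treating Week 12 as a simple mean of its records.
- Effect growing linearly to day 85: the shortfall on day d is 4 × (85 − d)/84, with mean 4 × 14/84 = 0.667 over days 58-84. Shift = 0.667k/(144 + k) = 0.012 to 0.023.
- No effect present at withdrawal: shift = 4k/(144 + k) = 0.071 to 0.140.

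Against 1.41 this is 0.8% to 9.9% of a standard error. With Visit 7 on day 54 or 60 and r = 1, the shifts are 0.029 or 0.019 (linear) and 0.154 or 0.125 (none).

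**Step 5: CGI-I.** k/2 = 1.3 to 2.6 records per arm of 80, or 1.6 to 3.3 percentage points if every one were a responder. This is an expected count; the documents do not fix how withdrawals split between arms.

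**Step 6: the label-kept reading.** Withdrawals on days 2-57 would then also sit at Week 12: 16r × 56/83 = 5.4 to 10.8 more records. With all 16 returning, 8 per arm, and carrying 0%, 50% or 100% of the effect, the difference is 4 × (72 + 8 × share)/80 = 3.6, 3.8 or 4.0. Power (normal approximation) is 0.77, 0.81 or 0.85, against 0.81 with 72 per arm.

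**Step 7: what an extra sensitivity run would show.** Removing withdrawal records before day 71 (midpoint of days 57 and 85) from Week 12, with r = 1, lowers the linear shift from 0.023 to 0.007 and the no-effect shift from 0.140 to 0.074. The estimate would be expected to move by about 0.02 to 0.07 points, under 5% of its standard error.

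**The case for a change.** The best case for a change is that a rule deciding which records form the main comparison belongs in the SAP before unblinding, and that one sentence would settle it. Step 6 supports this: if a programmer ignored 4.4 and kept every withdrawal record at Visit 8, the difference could fall by up to 0.4 points, far more than the mapped rule implies. The wording is also loose in places. If Visit 7 was missed and withdrawal came after day 71, the nearest visit is Visit 8 while the missed previous visit is Visit 7. The rule does not say that the telephone visits are ignored either.

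Part of this stands. The visible text has no cross-reference from the models to 4.4, and adding one would be tidy. But 4.4 belongs to the study-level considerations, and its mapping sentence is not itself restricted to summaries. The MMRM reports estimates by visit, so the study-level visit assignment is its natural input. The efficacy instruments are not given at telephone visits, so there is no efficacy visit there to fill. The definition may also appear in the MMRM code or the table specifications, which cannot be checked here.

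A sensitivity run on responders would be hard to read. The SAP 7.2.3 rule for everyone outside the responder group may mean only patients scored 3 to 7, and SAP 4.5 says missing values are not imputed unless stated. Removing records would change timing and missing-data handling together.

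**Conclusion.** No change follows. This is a gap in cross-referencing that analysts would fill sensibly by using the one visit assignment the SAP provides. After an attended Visit 7, mapping and the collected label give the same answer; for earlier withdrawals, 4.4 says what to do.

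Absence of a day limit is a fair trade-off: it keeps observed withdrawal data in the analysis, at an expected cost of 0.01-0.14 points on a 4-point difference, about 1-10% of the standard error. The upper end is not a bias if outcomes after stopping are meant to count, which fits the full analysis set in SAP 5.2.2, where patients stay in regardless of continued participation.

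The size rests on 10% withdrawal, even timing over days 2-84, earlier visits attended, 50-100% returning, and a simple mean in place of the MMRM. Heavier or later withdrawal would raise it. Protocol 13.6 and SAP 5.1 describe an exploratory trial from which no inferential decision is drawn, so a shift of this order would not alter how the result is read.
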